The initial data will also consist of baseline measurements of the outcome variables to establish baseline values. These will consist of the study's primary endpoints: the pain numerical rating scale (NRS, the traditional 0-10 pain score where 0 indicates no pain and 10 equates to the most intense pain imaginable), and the revised version of the short form McGill Pain Questionnaire. Additionally, the study's secondary endpoints will be collected: the self-report of the Leeds Assessment of Neuropathic Symptoms & Signs (s-LANSS), and the Pain Quality Assessment Scale (PQAS). The NRS is being used as it will allow us to compare our results with those of historical studies that only used this numerical score. Additionally, in the initial post-operative assessment, it is believed that subjects will not have yet recovered the mental faculties necessary for the more involved scales. The revised short form McGill Pain Score Questionnaire (sf-MPQ-2) is considered by many to be the "gold standard" pain questionnaire, especially for neuropathic pain. The s-LANSS has been shown to discriminate neuropathic from non-neuropathic pain; a score of greater than 12 is considered to be indicative of neuropathic pain (4). Finally, research has shown that the PQAS is able to assess pain changes during and as a result of treatment.

Intra-operative data recorded will include the total amounts of all medications documented on the Anesthesia Record, the surgical approach used (laparoscopic versus open), the type and location of the hernia being repaired, and details on any local anesthetic infusions used by the surgery team.

Follow-up data will be collected at six time points in person or over the phone per convenience including a) post-operative prior to Post Anesthesia Recovery Unit discharge, b) 18-36 hours post-operative, c) 1 months post-operative, d) 3 months post-operative, e) 6 months post-operative, and f) 12 months post-operative. Additional data collected will include details about analgesic use at all time points.

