The primary outcome is the overall incidence of CNP and will be compared across the three arms: TIVA-R, TIVA-K, and BIA protocol. This is a pilot study, as direct numbers for the estimation of the sample size are not available, given the varied incidence of chronic pain (10 to 63%) found in the literature, and the fact that anesthetic technique is typically not presented with this data. Because our hypothesis is that technique will affect CNP through the anesthetic technique's effect on the surgical stress response, we reviewed the literature surrounding this phenomenon. Significant differences in the circulating catecholamine concentration and in heart rate variability patterns has been observed in a study comparing BIA to TIVA (without specifying if ketamine or remifentanil were used) with 43 patients(6). The link between intraoperative stress and acute (24 hour postoperative) pain was demonstrated in a study of 34 subjects(11) using heart rate variability as a measure of stress, and in a study of 45 subjects using serum catecholamines(8). While this provides little guidance for technique's effect on chronic pain, it provides a starting point for pilot work. Therefore, we are targeting 48 patients, 16 in each group. Subject recruitment numbers will be closely monitored, and the randomization technique may be modified as the study nears completion to ensure balanced groups.

The surgical details and demographic data for each patient will be recorded on the data collection forms. This information will then be de-identified and entered into SPSS (v.21, SPSS, Inc., Chicago, IL.). SPSS is a program that performs statistical calculations. It resembles Microsoft Excel in terms of layout but is able to handle the advanced calculations required for statistical analysis.

Categorical data (demographics) will be tested with a Fisher's exact test (for 2x2 tables) or a Chi-square, both with two-sided tails. Continuous variables will be compared with a two-sample t-test. An overall p-value of 0.05 with Bonferroni or other relevant correction for multiple comparisons will be used for significance. If any of these vary significantly between the groups, multivariate techniques will be used instead of the univariate approach described below.

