All outcome variables (NRS, s-LANSS, PQAS, sf-MPQ) are ordinal data, and as such will require non-parametric testing. As the study is progressing, the techniques will be compared via Kruskal-Wallis testing at each time interval. The presence of CNP will be defined as a positive S-LANSS (scores ≥ 12 are highly suggestive of neuropathic pain); after the 3 month time point will be considered "chronic". These definitions are consistent with the literature and with published standards.(2,4) Thus, for the 6 and 12 month time points, the incidence of CNP for each technique will be computed and compared via chi-squared analysis.

Interim analyses are planned for 3, 6, 9 and 12 months, with the major focus being a definitive power analysis for variables found to be non-significant (as this is a pilot study). Because this study involves no changes to standard of care for herniorrhaphy surgery patients, stopping the study prematurely based on these interim analyses is not expected.

As planned, a continuous sampling of patients undergoing umbilical or inguinal herniorrhaphy will be included in this study. In addition, all equipment and personal required for this study are already in place within the VAPHS. Therefore, time for patient enrollment or equipment procurement is not necessary, and this study can begin as soon as all approvals (including IRB, R&D and ACOS) are granted. The study will continue for at least 1 year. The decision to continue past this time will be based on the achieved statistical power after 12 months of data collection. Because the data will be entered throughout the year and analyzed at 3 month

intervals, the time required for final analysis will be minimal. Submission for publication is expected within 3 to 12 months of the completion of data collection.

ID: Pro00000878

View: 5 Sub-Studies

1.0 * Is there a sub-study or are there sub-studies associated with this study?
There is no sub-study associated with this study.

ID: Pro00000878

View: 6 Study Population Summary

Study Population Summary

1.0 * What is the maximum number of subjects you plan to enroll at VAPHS?
60

2.0 * Do you plan on enrolling patients into different categories:
 Yes **No**

If yes, please explain:

3.0 If this is a multi-site study, indicate the projected total subject accrual:

4.0 * Please provide a justification for the sample size:

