When the patient presents on the day of surgery, [name] will review the patient's information, inquire about any health status or operative plan changes, and obtain informed consent. The patient's name will be added to the master list of subjects once they consent to screening. The master list of subjects will be stored electronically on the VAPHS network, and this list will only be viewable to the PI. The patient will then be randomized to one of three anesthetic technique protocols (TIVA-K, TIVA-R, or BIA) using a computer-generated random numbers table. Following this, the baseline information (including the demographics and pain survey scores included on the research study forms) will be collected.

IMPACT e-Consult

Instead of in-person consult for general surgery patients, e-consults are sometimes performed by the IMPACT team via phone for routine medical and functional evaluations prior to surgery. These include examining the electronic medical record for patient history and other evaluations in routine patient care that do not typically include the detailed pain status questionnaires to be used in this study. During the e-consults for hernia repair surgery, the IMPACT staff member will briefly state the following:

"Several of the physicians of our anesthesia department are interested in understanding how the amount of pain you feel after a surgery to repair a hernia can be influenced by the type of anesthesia medications you receive during your surgery. For this study, they would like to ask you questions about your pain both before and after your surgery (which they can do over the phone). If you are interested in participating in this study, please contact [name] at [contact] for more details."

The IMPACT staff member will not screen for study eligibility; all patients for hernia repair will be given this information. Patient contact with [name] is being requested due to her availability via telephone during business hours. If the patients are interested and contact [name], she will screen the patient's medical record to determine if the patient meets the study's inclusion and exclusion criteria and could be a potential candidate. If so, she will briefly describe the study as follows:

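### Covariate adjustment hangs on significance tests between randomised arms and an unnamed model, while the default comparison of the pain scales leaves their baseline scores unused

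*Combined protocol and SAP*

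**What the plan says.** All places are in the combined protocol and SAP.

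- **View 4.1, item 1.0.** Categorical patient variables are tested between arms by Fisher's exact or chi-square test. For the rest: "Continuous variables will be compared with a two-sample t-test". The threshold is: "An overall p-value of 0.05 with Bonferroni or other relevant correction for multiple comparisons will be used for significance". The consequence is: "If any of these vary significantly between the groups, multivariate techniques will be used instead of the univariate approach described below". The plan lists neither the variables in the tested family, nor the replacement model, nor its covariates.
- **Same item, default analyses.** For the scales: "As the study is progressing, the techniques will be compared via Kruskal-Wallis testing at each time interval". For CNP: "Thus, for the 6 and 12 month time points, the incidence of CNP for each technique will be computed and compared via chi-squared analysis". Neither has a baseline term.
- **View 4, item 1.0, Data Collection.** "The initial data will also consist of baseline measurements of the outcome variables to establish baseline values". This covers the numerical rating scale (NRS), the short-form McGill questionnaire, the s-LANSS and the PQAS.
- **View 8, item 2.0.** After consent and randomisation on the day of surgery: "Following this, the baseline information (including the demographics and pain survey scores included on the research study forms) will be collected".

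**The concern.** A significant difference between randomised arms is a chance event. Its p-value does not show whether the variable predicts the outcome, and only prediction makes adjustment worthwhile. The best candidate covariate for a pain score is normally the same score before surgery. The plan collects it and then leaves it out of the default test. It is also unclear whether baseline pain belongs to the tested variables at all, because the scales are classed as ordinal and handled separately.

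Two things are at stake: precision on the scales in a trial of 48 patients, and the fact that the data, not the plan, would choose the final model. The scales are not a side issue. View 4 introduces them with "These will consist of the study's primary endpoints: the pain numerical rating scale", although View 4.1 and View 6 name CNP incidence as the primary outcome.

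**Working it through.** **Inputs from the plan.** Three arms of 16, 3 × 16 = 48 (View 4.1); maximum enrolment 60 (View 6); alpha 0.05. No effect size, SD, dropout or baseline-to-outcome correlation is given, so there is no power figure to reproduce.

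**Assumptions.** One arm shifted by 0.8 SD; correlation r from 0 to 0.7; scores rounded and clipped to 0–10.

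**1. How often chance alone triggers the switch.** View 4 lists about eight patient variables. If independent and uncorrected: 1 − 0.95^8 = 33.7%. With Bonferroni: 1 − (1 − 0.05/8)^8 = 4.9%. The answer depends on a correction that the plan leaves open.

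**2. Whether the trigger finds imbalance.** A two-sample t-test at 16 v 16 detects a 0.5 SD baseline difference with power 28% at 0.05 and 8% at 0.05/8. In simulation about one trial in three has a pairwise baseline gap of at least 0.5 SD in a given score. A three-arm test of that score flags about 14% of those trials.

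**3. Precision available.** Adjustment multiplies the residual variance by 1 − r², and the equivalent size per arm is 16/(1 − r²).

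| r | 1 − r² | Equivalent n per arm |
|---|---|---|
| 0.3 | 0.91 | 17.6 |
| 0.5 | 0.75 | 21.3 |
| 0.7 | 0.51 | 31.4 |

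**4. Power with mid-range scores** (mean 4, SD 2; 60,000 simulated trials per setting; 16 per arm). Rank ANCOVA regresses the ranked outcome on arm and ranked baseline, with F on 2 and 48 − 4 = 44 degrees of freedom. The plan's rule is modelled here as a 0.05 test of baseline pain.

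| r | Kruskal-Wallis | Plan's rule | Always adjusted |
|---|---|---|---|
| 0 | 57.3% | 57.2% | 57.6% |
| 0.2 | 57.6% | 57.5% | 59.5% |
| 0.3 | 57.4% | 57.4% | 61.3% |
| 0.5 | 57.5% | 57.8% | 69.1% |
| 0.7 | 57.7% | 58.5% | 83.7% |

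If instead any of ten variables tested at an overall 0.05 triggers adjustment for baseline pain, power is 57.3–58.9%. If baseline pain is never tested or adjusted for, power is that of Kruskal-Wallis. Separate runs with similar rounded scores put the adjusted figures at 60–62%, 69–70% and 83–84% for r = 0.3, 0.5 and 0.7.

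Other settings, at those three correlations:
- 20 per arm: about 69% unadjusted against 73%, 80% and 92%.
- A 0.5 SD shift at 16 per arm: 25% against 28%, 32% and 43%.

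**5. Type I error over all trials.** The plan's rule gives 3.6–4.9%; always adjusting gives 5.0–5.3%.

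**6. Late follow-up with many zeros.** The background (View 2, item 4.0) cites chronic pain in 10–63% of patients after hernia repair. So 100 − 63 = 37% to 100 − 10 = 90% would be free of it. Taking those patients to score zero, the gain in percentage points at 16 per arm with a 0.8 SD latent shift is:

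| Zeros in unshifted arms | r = 0.3 | r = 0.5 | r = 0.7 |
|---|---|---|---|
| 77%, baseline equally near zero | about 1 | about 5 | about 13 |
| 89%, baseline equally near zero | about 1 | about 2 | about 7 |

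Runs differ by about a point. If baseline scores are mid-range and only the late scores sit at zero, the gains are about 2, 7 and 16 points (77% zeros) and 2, 5 and 10 points (89% zeros).

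**The case against.** The strongest reply has four parts.

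- **The named primary outcome is CNP incidence, and the fix leaves its comparison alone.** This stands. The gain is for the scales.
- **Randomisation keeps the unadjusted tests valid, and this is a pilot.** Validity stands. Pilot status does not favour discarding data already collected, least of all when the results are meant to support a larger study (View 7.1).
- **The benefit depends on a correlation that the documents do not give.** This stands. Low values are plausible, because chronic pain syndromes are excluded (View 6.1) and follow-up runs to 12 months.
- **The mid-range figures flatter late follow-up.** This also stands, so the two situations are reported separately.

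Three stronger readings are tempting, and the documents do not support them.

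- A reader might infer that testing before adjusting inflates the false-positive rate. In the simulations it does not. Among trials with a baseline gap of at least 0.5 SD, Kruskal-Wallis does reject too often (6.2%, 7.2% and 9.9% at r = 0.3, 0.5 and 0.7), but that error is conditional on the imbalance. Over all trials the test keeps its level.
- A reader might hold that a two-sample t-test cannot serve three arms. The plan's next sentence allows a multiplicity correction, so corrected pairwise tests are a workable reading.
- A reader might take Kruskal-Wallis at each interval to include baseline and so to deal with it. That would be one more baseline test, not an adjustment.

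**Conclusion.** The point holds as an inexpensive improvement, not as a failure of validity. The significance rule recovers almost none of whatever precision the baseline scores offer, and it leaves the final model to the data.

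Under the stated assumptions, the gain from always adjusting mid-range scores, likeliest at the acute time points, is roughly 4, 12 and 26 percentage points at r = 0.3, 0.5 and 0.7. It is about 1, 2–5 and 7–13 points if most patients, at baseline as well as late follow-up, score near zero. It is negligible at r of 0.2 or less, with no measurable loss at r = 0. The larger figures should not be carried over to 6 and 12 months or to the CNP comparison. The unnamed model needs fixing whatever the correlation.

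**What to change.** In View 4.1, item 1.0:

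1. Delete the significance rule, and describe baseline characteristics by arm without tests.
2. Pre-specify that each pain scale, at each time point where it is collected, is compared across the three arms with its own pre-operative score as the covariate, whatever the baseline p-values. Rank ANCOVA suits the plan's treatment of the scales as ordinal.
3. Keep the planned comparison of binary CNP as primary, because events may be few in 48 patients.

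In View 8, item 2.0, and the matching consent text in View 9.4: baseline scores are recorded after randomisation, and the abstract in View 2 states only that patients are blinded. Have the scores recorded before the allocation is revealed to the person recording them, or state this as a limitation of the adjusted analysis.

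The cost is a change of SAP wording, slightly more analysis work, one more model assumption, and a change in the order of steps on the day of surgery. No new data are needed.

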A total of 48 patients undergoing either inguinal (including femoral) or ventral (including umbilical) herniorrhaphy that requires general anesthesia in the operating room will be enrolled in the study with continuous sampling beginning as soon as the protocol is approved. Inguinal hernias will be the focus, as they are thought to have a higher incidence of chronic pain; however, ventral herniorrhaphy may also be used if required to meet study goal numbers. A patient will be considered enrolled in the study when they have passed initial screening questions, signed the consent form, and been randomized to one of three anesthetic technique protocols (TIVA-K, TIVA-R, or BIA). 16 subjects will be used in each group. At the time of first subject enrollment, the subjects will be divided amongst the three groups using a random assignment table generator (www.graphpad.com/quickcalcs/randomize2) stating that A will equal TIVA-K, B will equal TIVA-R, and C will equal BIA. The results will be recorded and followed for all subsequently enrolled patients.

Consistent with our current standard of care, all protocols will begin with perphenazine (up to 8 mg) and acetaminophen (up to 1300 mg) by mouth in the pre-operative holding area, and premedication prior to induction with up to 2 mg of midazolam.

The TIVA-K protocol will consist of the induction of anesthesia with propofol (1-2.5 mg/kg) and ketamine (20 mg), with muscle relaxation being accomplished with either succinylcholine or rocuronium as necessary. Endotracheal intubation may be used for airway management. Anesthesia will be maintained with a propofol infusion (50-150 mcg/kg/min), lidocaine infusion (0.5-1 mg/kg/hr), and ketamine (5 mg each half hour to a maximum of 50 mg). Standard antiemetic medications will be given.

The TIVA-R protocol will consist of the induction of anesthesia with propofol bolus (1-2.5 mg/kg) and the initiation of a remifentanil infusion (0.05-2 mcg/kg/min). Muscle relaxation will be accomplished with either succinylcholine or rocuronium as necessary. Endotracheal intubation may be used for airway management. Anesthesia will be maintained with a propofol infusion (50-150 mcg/kg/min), lidocaine infusion (0.5-1 mg/kg/hr), and continuation of the remifentanil infusion (0.05-2 mcg/kg/min). Standard antiemetic medications will be given.

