This waiver is only being requested for screening and recruitment purposes. Patient involvement will be considered complete after the final questionnaires are administered 12 months after surgery. The results of the study will then be compiled, analyzed, described, and published. While any practical effect the type of anesthesia each individual patient received would have little impact on the patient's future medical history, the study's published results will be available electronically.

ID: Pro00000878

View: 9.3 Waiver of Documentation of Informed Consent

Waiver of Documentation of Informed Consent**You have selected a waiver of Documentation of Informed Consent****1.0 This is a request for Waiver of Documentation of Informed Consent because this research study conforms to either A and/or B (Check if 'yes' and provide the verifying information requested):**

* A: The only record linking the subject and the research would be the consent document and the principal risk would be potential harm resulting from a breach of confidentiality. Each subject will be asked whether the subject wants documentation linking the subject with the research, and the subject's wishes will govern. Yes No

AND/OR

* B: The proposed study poses minimal risk to the subjects. Yes No

If yes, please explain why the proposed study poses minimal risks to the subjects. (Outline the subject's involvement in the project and why the study poses minimal risk) :

This study will pose minimal risk to the subjects since all anesthetic techniques are within the standards of best practice for patients undergoing herniorrhaphy with general anesthesia. The proposed intervention will not alter surgical modality as previously determined by the treating physician. The backbone of the study is the collection of the data via the survey instruments, which carries only the very rare risk for a breach of confidentiality. The precautions detailed in the risk section will be used to minimize this risk.

2.0 * The research involves no procedures for which written consent is normally required outside of the research context. Research procedures include:

For this waiver, the procedures only include the sharing of information of interested patients with the PI so that he can contact the potential subject and further describe the study. All subjects that participate in the full study will review and sign an informed consent document.

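### The calendar looks and the 12-month continuation rule come before the chronic pain outcome they are meant to inform

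*Combined protocol and SAP*

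**What the plan says.** View 4.1 (analysis plan, item 1.0) names the overall incidence of CNP, compared across three arms, as the primary outcome. It tests CNP by chi-squared at the 6- and 12-month time points, which are counted from surgery.

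The same item sets the timetable: "Interim analyses are planned for 3, 6, 9 and 12 months". The main stated purpose of these looks is a conclusive power analysis for variables that have not reached significance. On duration it says "The study will continue for at least 1 year", and then: "The decision to continue past this time will be based on the achieved statistical power after 12 months of data collection". It does not say which variable's power, or what level of power, decides.

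View 4 (item 1.0) describes entry as "continuous sampling beginning as soon as the protocol is approved". View 9.2 (item 5.0) fixes the end of each patient's follow-up: "Patient involvement will be considered complete after the final questionnaires are administered 12 months after surgery".

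**The concern.** The looks run on study time, whereas the outcome runs on each patient's own time since surgery. With staggered entry the two clocks differ by the patient's entry date. A look at study month 12 therefore sees a 12-month outcome only for someone operated on at the very start.

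Two things are at stake. First, a power analysis at these looks cannot be conclusive for the primary outcome, because that outcome is absent or only partly observed. Second, the decision to continue rests on such a figure. If power looked adequate on early pain scores or partial 6-month data, the study could be ended before 12-month CNP had been observed.

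The early looks also have a cost. View 4.1 compares the techniques while the study is in progress. View 2 describes the study as patient-blinded, View 10.0.1 has the principal investigator contact patients for the 1- to 12-month surveys, and View 11 provides no data monitoring committee. By-arm results would thus reach the person still collecting self-reported outcomes.

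**Working it through.** **Plan's own figures.** 3 arms × 16 = 48 patients, which agrees with the stated total. The plan gives no effect size, target power or accrual rate, so there is no power or timeline calculation to reproduce.

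**Which clock the looks use.** View 4.1 says "Because the data will be entered throughout the year and analyzed at 3 month" intervals, and the follow-up schedule in View 4 (before recovery-unit discharge, 18–36 hours, then 1, 3, 6 and 12 months) has no 9-month survey. A 9-month look can therefore only mean study month 9.

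**Rule.** A patient operated on at study month t has the k-month result at look m only if t + k ≤ m.

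**Count.** With 48 patients accrued uniformly over A months, the number with the k-month result at look m is

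N = 48 × max(0, min((m − k)/A, 1)).

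A is not in the documents. I assume 6, 12 and 18 months to show the range.

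Six-month CNP (k = 6):

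| A (assumed) | month 3 | month 6 | month 9 | month 12 |
|---|---|---|---|---|
| 6 | 0 | 0 | 48 × 3/6 = 24 | 48 × 6/6 = 48 |
| 12 | 0 | 0 | 48 × 3/12 = 12 | 48 × 6/12 = 24 |
| 18 | 0 | 0 | 48 × 3/18 = 8 | 48 × 6/18 = 16 |

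Twelve-month CNP (k = 12): m − k is at most 12 − 12 = 0, so the count is 0 at every look for every A.

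Three-month scores (k = 3) at months 3/6/9/12: 0/24/48/48 for A = 6, 0/12/24/36 for A = 12 and 0/8/16/24 for A = 18.

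**Boundary.** A patient operated on exactly on day 0 reaches 6 months on the day of the month-6 look and 12 months on the day of the month-12 look. Under uniform accrual this adds at most about one patient. Only if all 48 had surgery on day 0 would both outcomes be complete at those looks. No visit window is stated for the 6- or 12-month surveys.

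**What the month-12 decision would rest on.** With A = 12 and equal arms, 24/3 = 8 patients per arm have 6-month CNP. Applying the plan's literature range for chronic pain of 10% to 63%, the expected events across all three arms are 24 × 0.10 = 2.4 to 24 × 0.63 = 15.1.

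**When 12-month CNP is complete for all 48.** A + 12 gives study month 18, 24 or 30.

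**The case against.** The best defence is that this is a declared pilot. View 4.1 does not expect early stopping, and the power analysis covers several variables rather than CNP alone. View 4 calls the numerical rating scale and the short-form McGill questionnaire primary endpoints, and both are collected early, so the first looks are not empty. That stands, and it limits the point to CNP.

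Three stronger readings are tempting, but the documents do not support them.

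- *The study ends at 1 year and its final analysis has no 12-month data.* One year is a minimum, the month-12 analysis is listed as interim, and 12-month surveys are promised throughout. Publication is timed from the completion of data collection. The remark that "the time required for final analysis will be minimal" concerns analysis effort and does not set a cut-off.
- *The plan assumes that enrolment takes no time.* The words "time for patient enrollment or equipment procurement is not necessary" follow a statement that equipment and staff are in place and lead into one that work can start on approval. The natural meaning is that no start-up period is needed.
- *The looks can compare only acute scores.* Some 3-month scores exist from month 6, and the brief description in View 0.0 counts 3 months as chronic. Partial 6-month CNP exists from month 9.

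It can also be said that ending the study under the rule might mean ending enrolment only, with follow-up completed. The plan does not say so, which is itself a reason to rewrite the sentence.

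**Conclusion.** The point holds for the looks and the continuation rule. Under any staggered accrual, and apart from a day-0 patient, 6-month CNP is missing at the looks in months 3 and 6, and 12-month CNP is missing at all four. That result needs no assumption about the accrual rate. How much 6-month CNP is available at month 12 does depend on it: all 48 patients if accrual takes 6 months, half of them at 12 months, and one third at 18 months.

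The looks can describe acute, 1-month and 3-month scores and, later, part of the 6-month outcome. They cannot deliver a conclusive power analysis for the primary outcome. The continuation rule allows the study to end before 12-month CNP exists, though it does not require it. This should be corrected in the text; it does not invalidate the design.

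**What to change.** Change View 4.1, item 1.0, in three places:

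1. Replace the continuation rule based on power at 12 months with a fixed end of study: planned enrolment completed, plus 12 months after the last randomised patient's surgery.
2. Limit the calendar looks to recruitment, survey completion and CNP counts pooled over arms. The by-arm comparisons of pain scores would then no longer be made at these looks.
3. Compare CNP between arms at 6 months once all randomised patients have passed 6 months, and at 12 months once all have passed 12 months.

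It would also help to reword the remark about enrolment time so that it plainly refers to start-up.

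The cost is a later stated completion date (accrual plus 12 months, so month 18, 24 or 30 under the assumed accrual periods) and no early between-arm results. No extra patients or visits are needed.
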